#### 3.1.2 Inadequate Response

Inadequate response is defined by having < 20% improvement in their tender and < 20% in their swollen joint counts from baseline at or after week 24. This will be calculated automatically based on the joint count. Inadequate response may be assessed at a

regularly scheduled visit or at a disease assessment visit as described in [Section 7.2.5](#). All subjects that initiate rescue treatment must complete a disease assessment follow-up visit 4 weeks later to monitor for labs (see [Section 7.2.5](#) and [Table 1](#)).

Subjects randomized to the etanercept plus methotrexate arm that have an inadequate response will continue to receive the same treatment.

### **3.2 Number of Sites**

Approximately 105 sites globally will participate in the study. Additional sites may be added if necessary. Sites that do not enroll subjects within 3 months of site initiation may be closed.

### **3.3 Number of Subjects**

Participants in this clinical investigation shall be referred to as “subjects”.

The number of subjects expected to be enrolled in the study is 840. There will be approximately 280 subjects per treatment arm.

Sample size considerations are provided in [Section 10.2](#).

### **3.4 Replacement of Subjects**

Subjects who are withdrawn or removed from treatment or the study will not be replaced.

### **3.5 Estimated Study Duration**

#### **3.5.1 Study Duration for Subjects**

The study will consist of up to a 30-day screening, a 48-week double-blind treatment period, and a 30-day safety follow-up period. The maximal duration of trial participation for an individual subject is approximately 56 weeks including the screening and safety follow-up telephone call.

#### **3.5.2 End of Study**

End of study is defined as the time when the last subject is assessed or receives an intervention for evaluation in the study.

## **4. SUBJECT ELIGIBILITY**

Investigators will be expected to maintain a screening log of all potential study candidates that includes limited information about the potential candidate (eg, date of screening).

Before any study specific activities/procedure, the appropriate written informed consent must be obtained (see [Section 11.1](#)).

#### 4.1 Inclusion and Exclusion Criteria

##### 4.1.1 Inclusion Criteria

101. Subject has provided informed consent prior to initiation of any study-specific activities/procedures.
102.  $\geq 18$  years of age at screening
103. subject has had a diagnosis of PsA by the Classification Criteria for Psoriatic Arthritis (CASPAR) criteria
104. subject has  $\geq 3$  tender and  $\geq 3$  swollen joints (as part of a 68/66 joint count) at screening and at baseline
105. subject has an active psoriatic skin lesion (at least one psoriatic plaque approximately 2 cm or more in diameter)
106. subject is naïve to etanercept and any other biologic for the treatment for PsA or psoriasis
107. subject has no prior use of methotrexate for PsA. Prior treatment with methotrexate is allowed if indicated for psoriasis as long as discontinuation was not due to toxicity or intolerance and treatment discontinued  $\geq 6$  months prior to initiation of investigational product
108. for subjects receiving non-steroidal anti-inflammatory drugs (NSAIDs) (including as needed use [PRN]): the dose must be stable for  $\geq 2$  weeks prior to initiation of investigational product
109. for subjects receiving oral corticosteroids: the dose must be stable (not to exceed the equivalent of 10 mg of prednisone per day) for  $\geq 4$  weeks prior to initiation of investigational product
110. negative test for hepatitis B surface antigen, hepatitis B core antibody and hepatitis C antibody
111. no known history of active tuberculosis
112. National guidelines should be followed for appropriate tuberculosis screening in the setting of anti-TNF therapy, including a minimum of:
  - subject has a negative test for tuberculosis during screening defined as either:
    - negative purified protein derivative (PPD) ( $< 5$  mm of induration at 48 to 72 hours after test is placed) OR
    - negative Quantiferon test.

subjects with a positive PPD and a history of Bacillus Calmette-Guérin vaccination are allowed with a negative Quantiferon test.

subjects with a positive PPD test (without a history of Bacillus Calmette-Guérin vaccination) or subjects with a positive or indeterminate Quantiferon test are allowed if they have ALL of the following:

- no symptoms per tuberculosis worksheet provided by Amgen Inc.
- documented history of a completed course of adequate treatment or prophylaxis per local standard of care prior to the start of investigational product

- no known exposure to a case of active tuberculosis after most recent prophylaxis
  - no evidence of active tuberculosis on chest radiograph within 3 months prior to the first dose of investigational product
113. subject, if female and not at least 2 years postmenopausal or history of hysterectomy, bilateral salpingectomy, or bilateral oophorectomy, has a negative serum pregnancy test  $\leq$  4 weeks from starting investigational product and a negative urine pregnancy test at baseline (day 1)

#### 4.1.2 Exclusion Criteria

##### *Medical Conditions*

201. subject has known history of alcoholic hepatitis, nonalcoholic steatohepatitis or immunodeficiency syndromes, including Human Immunodeficiency Virus infection.
202. subject has any active infection (including chronic or localized infections) for which anti-infectives were indicated within 4 weeks prior to the first dose of investigational product.
203. subject has a serious infection, defined as requiring hospitalization or intravenous anti-infectives within 8 weeks prior to the first dose of investigational product.
204. subject had prosthetic joint infection within 5 years of screening or native joint infection within 1 year of screening.
205. subject has known alcohol addiction or dependency, uses alcohol daily, or has current substance use or abuse.
206. subject has one or more significant concurrent medical conditions per investigator judgment, including the following:
- poorly controlled diabetes
  - chronic kidney disease stage IIIb, IV, or V
  - symptomatic heart failure (New York Heart Association class II, III, or IV)
  - myocardial infarction or unstable angina pectoris within the past 12 months prior to randomization
  - uncontrolled hypertension
  - severe chronic pulmonary disease (eg, requiring oxygen therapy)
  - multiple sclerosis or any other demyelinating disease
  - major chronic inflammatory disease or connective tissue disease other than PsA (eg, systemic lupus erythematosus with the exception of secondary Sjogren's syndrome)

##### *Excluded Medications*

207. prior or current use of cyclophosphamide, chlorambucil, nitrogen mustard, or any other alkylating agent.

208. subject has used any of the following  $\leq$  3 months prior to screening:
- abatacept
  - anakinra
  - azathioprine
  - cyclosporine
  - gold
  - mycophenolate mofetil
  - ProSORBA column
  - Systemic tacrolimus
  - Otezla (apremilast)
209. subject has used leflunomide  $\leq$  12 weeks prior to screening
210. subject has used any of the following  $\leq$  4 weeks prior to screening:
- sulfasalazine
  - intraarticular, intramuscular or intravenous corticosteroids, including adrenocorticotrophic hormone
  - intraarticular hyaluronic acid injections
  - live vaccines
211. for subjects not on continuous analgesics, subject has taken the following within 12 hours prior to screening: acetaminophen, NSAID, hydrocodone, codeine, tramadol, propoxyphene and/or oxycodone (unless in the form of oxycontin). For subjects not on continuous analgesics, subject has taken oxycontin within 24 hours prior to screening.

*Laboratory Abnormalities*

212. Subject has laboratory abnormalities during screening, including the following:
- Aspartate aminotransferase (AST) and/or alanine aminotransferase (ALT)  $>$  1.5 x the upper limit of normal (ULN)
  - Platelet count  $<$  125,000/mm^3
  - White blood cell count  $<$  3,000 cells/mm^3
  - Absolute neutrophil count  $<$  1500/mm^3
  - Estimated creatinine clearance  $<$  50 mL/min (Cockcroft-Gault formula, calculated value to be provided to sites)
213. Subject has any other laboratory abnormality, which, in the opinion of the investigator poses a safety risk, will prevent the subject from completing the study, or will interfere with the interpretation of the study results.

*Other*

214. Female subject is not willing to use highly-effective methods of birth control during treatment and for 6 months after the end of treatment (except if at least 2 years postmenopausal or surgically sterile [hysterectomy, bilateral oophorectomy, or bilateral salpingectomy] or has had a bilateral tubal ligation).
215. Male subject with a partner of child-bearing potential is not willing to use a condom during treatment and for 6 months after the end of treatment (except for men who are surgically sterile).
216. Male subject with a pregnant partner, who is not willing to use a condom to prevent exposure of the fetus to semen during treatment and for 6 months after the end of treatment.
217. Subject is pregnant or breastfeeding, or planning to become pregnant or breastfeed while enrolled in the study, up to the subject's last visit and for 6 months after the end of treatment.
218. Malignancy, except adequately treated non-melanoma skin cancers, cervical or breast ductal carcinoma in situ with no evidence of disease within the last 5 years.
219. Subject has known sensitivity to any of the products or components to be administered during dosing.
220. Subject likely to not be available to complete all protocol-required study visits or procedures, and/or to comply with all required study procedures (eg, PROs) to the best of the subject and investigator's knowledge.
221. History or evidence of any other clinically significant disorder, condition or disease (with the exception of those outlined above) that, in the opinion of the investigator or Amgen physician, if consulted, would pose a risk to subject safety or interfere with the study evaluation, procedures or completion.
222. Currently receiving treatment in another investigational device or drug study, or participated in any study involving administration of an investigational drug or device within 30 days or 5 terminal elimination half-lives, whichever is longer, before enrollment.
223. Other investigational procedures while participating in this study are excluded.

## **5. SUBJECT ENROLLMENT**

Before subjects begin participation in any study-specific activities/procedures, Amgen requires a copy of the site's written institutional review board/independent ethics committee (IRB/IEC) approval of the protocol, informed consent form, and all other subject information and/or recruitment material, if applicable (see [Section 11.2](#)). All subjects must personally sign and date the informed consent form before commencement of study-specific activities/procedures.

A subject is considered enrolled when the investigator decides that the subject has met all eligibility criteria. The investigator is to document this decision and date, in the subject's medical record and in the enrollment CRF.

Each subject who enters into the screening period for the study (defined as the point at which the subject signs the informed consent form) receives a unique subject identification number before any study-related activities/procedures are performed. The subject identification number, assigned by the Interactive Voice Response System (IXRS), will be used to identify the subject throughout the clinical study and must be used on all study documentation related to that subject. The subject identification number must remain constant throughout the entire clinical study; it must not be changed after initial assignment, including if a subject is re-screened. This number will not necessarily be the same as the randomization number assigned for the study.

Subjects not meeting eligibility criteria are permitted to re-screen twice (see [Section 7.2.1](#) and [7.2.2](#)).

### **5.1 Randomization/Treatment Assignment**

Subjects that meet all eligibility criteria will be randomized at baseline to receive etanercept plus methotrexate, etanercept plus placebo for methotrexate or methotrexate plus placebo for etanercept in a 1:1:1 ratio via IXRS. Assignment to the treatment arms will be based on a computer generated randomization schedule prepared by Amgen before the start of the study. Each randomized subject will receive a single, unique randomization number at randomization. The randomization date is to be documented in the subject's medical record and on the enrollment CRF.

### **5.2 Site Personnel Access to Individual Treatment Assignments**

A subject's treatment assignment should only be unblinded when knowledge of the treatment is essential for the further management of the subject on this study. In the event that a subject's treatment assignment must be unblinded by the investigator the subject will not be allowed to receive any further investigational product. Refer to the Investigational Product Instruction Manual (IPIM) for a description regarding how responsible pharmacists and investigators will access treatment information via IXRS in the event that there is a need to break the treatment blind.

Other than rescue therapy situations, in the event of inadvertent unblinding (ie, the blind was not intended to be broken as described above), the investigator should immediately notify Amgen. Each scenario will be reviewed individually to determine if the impacted subject(s) are able to continue receiving investigational product.

Unblinding at the study site for any other reason, including the scenarios described above, will be considered a protocol deviation. The investigator is strongly encouraged

to contact the Amgen **Global Clinical Trial** Manager before unblinding any subject's treatment assignment. If not possible, the investigator must inform Amgen within 1 working day after the event.

## **6. TREATMENT PROCEDURES**

### **6.1 Classification of Products and/or Medical Device(s)**

The Amgen Investigational Product used in this study includes: etanercept or placebo for etanercept.

The non-Amgen Investigational product used in this study includes: methotrexate or placebo for methotrexate.

The non-Amgen non-investigational product used in this study includes: folic acid.

The IPIM, a document external to this protocol, contains detailed information regarding the storage, preparation, and administration of etanercept, methotrexate, and folic acid.

### **6.2 Investigational Product**

#### **6.2.1 Amgen Investigational Product: Etanercept**

Etanercept will be manufactured and packaged by Amgen Inc. and distributed using Amgen clinical study drug distribution procedures. Etanercept will be supplied in a single-use pre-filled 1mL syringe as a sterile, preservative-free solution for subcutaneous injection. The solution of etanercept is clear and colorless and is formulated at pH [CCI]. Each single-use pre-filled syringe (PFS) contains 0.98 mL of 50 mg/ml etanercept in a formulation consisting of [CCI]mM sodium chloride, [CC]mM sodium phosphate, [CC]mM L-arginine-HCL, and [CC] sucrose. Etanercept will be provided with 4 syringes to a pack. Placebo will be presented in identical containers and stored/packaged the same as etanercept.

#### **6.2.1.1 Dosage, Administration, and Schedule**

Etanercept dosing in the study will follow the recommended label dosing for subjects with PsA (subcutaneous injection, 50 mg once weekly). The treatment period of this study is 48 weeks. Etanercept will be provided as a 50 mg PFS (0.98 mL of a 50-mg/mL solution of etanercept). Each dose of investigational product will consist of the complete contents of 1 syringe. The injection site should be rotated with each dose. Subjects will receive 1 dose of etanercept per week (scheduled approximately 7 days apart) for 48 weeks. Throughout the entire trial, administration of etanercept should occur on the scheduled dose day; however, if unavoidable, it may be given earlier or later as long as the dose is not within 2 days of the next scheduled dose. If the dosing window is

missed, that dose should be skipped and the reason for the missed dose must be reported on the electronic case report form (eCRF). Subsequent doses of investigational product should resume on the original schedule. If etanercept is to be taken the day of a study visit, it must be taken after the study visit has occurred (ie, at the subject's location on the scheduled dose day).

Injections of etanercept will be administered by the subject or a caregiver. The individual administering the dose must demonstrate to the site staff that he or she is competent to correctly administer the subcutaneous doses. The first dose of etanercept must be administered at the study site. All subsequent doses will be administered at the subject's location on the scheduled dose day. Supplies of etanercept will be dispensed to subjects for administration at home. The site will instruct the subject in appropriate handling and storage of used and unused syringes and documentation of dosing in the subject diary. The start date, quantity administered and box number of investigational product are to be recorded in each subject's eCRF. Please refer to the Investigator's Brochure for the most recent safety information. A link to the United States Prescribing Information can be found in the Investigator's Brochure.

### **6.2.2 Non-Amgen Investigational Product: Methotrexate**

Non-Amgen investigational product methotrexate will also be used in this study. Methotrexate will be distributed using Amgen clinical trial drug distribution procedures. Methotrexate will be supplied as 2.5 mg methotrexate capsules or as matching placebo capsules. For those subjects receiving rescue therapy, methotrexate will be dispensed as 2.5 mg tablets.

Additional details regarding the product(s) are provided in the IPIM.

#### **6.2.2.1 Dosage, Administration, and Schedule**

Methotrexate dosing will be initiated at 10 mg weekly and will be titrated up to a final dose of 20 mg weekly over a 4-week period. The treatment period for this study is 48 weeks. Methotrexate will be provided as 2.5 mg capsules, or as placebo capsules, and will be taken once weekly by oral administration. Capsules should be swallowed whole. Subjects will receive 1 dose of methotrexate or placebo per week (scheduled approximately 7 days apart) for 48 weeks. Throughout the entire trial, administration of methotrexate or matching placebo should occur on the scheduled dose day; however, if unavoidable, it may be given earlier or later as long as the dose is not within 4 days of the next scheduled dose. If the dosing window is missed, that dose should be skipped and the next dose should be resumed at the scheduled time. The reason for the missed

dose must be reported on the eCRF. Double or extra doses should not be taken. The start date, quantity administered, and bottle/package number of methotrexate is to be recorded on the subject's diary and entered into the eCRF.

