This study will also aim to characterize the response rates of etanercept on enthesitis, dactylitis, and psoriatic nail changes. The PRESTA trial, assessed two different regimens of etanercept (50 mg twice weekly or 50 mg once weekly) in subjects with psoriasis and PsA. Etanercept 50 mg once weekly resulted in a 70.0% and 81.3% improvement from baseline in enthesitis at week 12 and 24 respectively. Similarly, improvement in dactylitis from baseline at weeks 12 and 24 were 78.4% and 84.8%, respectively (Sterry et al, 2010). There is a paucity of data regarding the efficacy of methotrexate monotherapy on dactylitis and enthesitis in patients with PsA. A recent study looking at the effect of etanercept on the Nail Psoriasis Severity Index (NAPSI) score at week 12 and 24 improved by 50% and 72%, respectively on a weekly dose of Enbrel of 50 mgs (Ortonne et al, 2013). In another recent study comparing improvement in nail changes on methotrexate monotherapy compared to cyclosporine monotherapy, methotrexate demonstrated a 30% improvement at 12 weeks and a 54% improvement at 24 weeks in the NAPSI score (Gümüşel et al, 2011).

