#### **6.2.2.2 Dosage Adjustments, Delays, Rules for Withholding or Restarting, Permanent Discontinuation**

Methotrexate (or placebo for methotrexate) will be initiated at a dosage of 10 mg weekly at week 0 (day 1). The dose will be increased by 2.5 mg weekly up to 20 mg over a 4 week period. In cases of typical methotrexate toxicities (eg, increased aspartate transaminase or alanine transaminase, or gastrointestinal adverse effects, severe stomatitis), the methotrexate dose may be reduced up to 10 mg weekly. The reason for dose change of methotrexate is to be recorded on each subject's eCRF.

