### 7.2.3 Baseline Visit (Day 1)

Subjects meeting all eligibility criteria will be randomized by IXRS as described in [Section 5](#). The date of first dose of blinded investigational product is defined as day 1 week 0. All subsequent doses and study visits will be scheduled based on the

day 1 date. Following the first blinded dose, investigational products and related supplies will be dispensed to the subject for self-administration per [Table 1](#).

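### The methotrexate dosing window limits how late a dose may be taken but not how early, so two 20 mg doses can fall 1 to 2 days apart and still meet it

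*Protocol*

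**What the plan says.** Protocol section 6.2.2.1 sets a weekly schedule: "Subjects will receive 1 dose of methotrexate or placebo per week (scheduled approximately 7 days apart) for 48 weeks". Doses belong on the scheduled day. If a departure is unavoidable, "it may be given earlier or later as long as the dose is not within 4 days of the next scheduled dose". A dose that misses this window is skipped and dosing resumes on schedule. The section adds: "Double or extra doses should not be taken".

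Section 7.2.3 fixes the calendar: "All subsequent doses and study visits will be scheduled based on the" day 1 date. A shifted dose therefore does not move the ones after it. The same section has subjects administer the dispensed product themselves.

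Section 6.2.2.2 covers titration from 10 mg to 20 mg and toxicity, for which "the methotrexate dose may be reduced up to 10 mg weekly". It gives no interval between doses. Section 6.1 refers to the IPIM, an external document that "contains detailed information regarding the storage, preparation, and administration of etanercept, methotrexate, and folic acid". The etanercept rule in section 6.2.1.1 has the same form with a smaller number: "it may be given earlier or later as long as the dose is not within 2 days of the next scheduled dose". The SAP states no minimum interval.

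**The concern.** The rule allows movement in both directions but measures distance in only one. Taking a dose later shortens the time to the next scheduled dose, so lateness is limited. Taking it earlier lengthens that time, so the condition is met however early the dose is. The interval that matters for tolerability is the one since the last dose actually taken, and the rule does not mention it.

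The rule's own design shows that spacing matters. It gives up a dose rather than let it fall too close to the next one, and its limit for methotrexate is 4 days against 2 for etanercept. The protocol also treats methotrexate toxicity as dose-related, through slow titration and the permitted reduction. A rule that keeps about 4 to 5 days between doses on the late side should not admit two full doses within 1 to 2 days on the early side.

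Two of the three arms, about 2 x 280 = 560 of 840 subjects, take active methotrexate from the start. Rescued etanercept-monotherapy subjects take it from rescue. Diary dates would show a short interval only afterwards. From week 24, scheduled diary review and safety laboratory tests are 12 weeks apart (weeks 24, 36 and 48 in Table 1), apart from any disease assessment visits.

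**Working it through.** **Inputs.** From section 6.2.2.1: doses 7 days apart, the 4-day limit, and a 20 mg maintenance dose. From section 7.2.3: the schedule stays anchored to day 1. Whole days are used.

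**Set-up.** Let three consecutive doses be scheduled on days 0, 7 and 14. The first is taken d days late and the second e days early.

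- Distance from the first dose to its next scheduled dose: 7 - d.
- Distance from the second dose to its next scheduled dose: 14 - (7 - e) = 7 + e.
- Gap between the two doses actually taken: 7 - d - e.

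**Late side.** If exactly 4 days is allowed, 7 - d >= 4 gives d <= 3. If exactly 4 days counts as within the limit, 7 - d > 4 gives d <= 2. With the second dose on time (e = 0), the gap is at least 7 - 3 = 4 days or 7 - 2 = 5 days. This is the floor that the rule appears to intend.

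**Early side.** The condition is 7 + e >= 4 (or > 4), which holds for every e >= 0. There is no limit.

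**Gaps that meet the condition**

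| First dose | Second dose, days early | Gap, days |
|---|---|---|
| On time (d = 0) | 4, 5, 6 | 3, 2, 1 |
| 2 days late | 1, 2, 3, 4 | 4, 3, 2, 1 |
| 3 days late (only if exactly 4 is allowed) | 1, 2, 3 | 3, 2, 1 |

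In the first row the early dose is still 11, 12 or 13 days before its next scheduled dose.

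**If sites assume a symmetric window.** Suppose earliness were capped at the lateness limit, although the text does not say so. With d and e each from 0 to 3, 6 of 16 pairs give a gap below 4 days (3, 3, 2, 3, 2, 1). With d and e each from 0 to 2, 3 of 9 pairs give a gap below 5 days (4, 4, 3). These count combinations and are not probabilities.

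**If the next scheduled dose means the first scheduled day after the dose is actually taken.** A day-7 dose taken on day 4, 5 or 6 is then 3, 2 or 1 days from day 7 and is barred. The same dose taken on day 1 or 2 is 6 or 5 days from day 7 and passes. Gaps of 1 and 2 days after an on-time day-0 dose still meet the condition, while the milder early shifts do not.

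**Exposure.** Two maintenance doses are 2 x 20 = 40 mg within the gap, against 20 mg per 7 days. The total number of doses is unchanged.

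**The case against.** The strongest reply is that the clause should be read with its neighbours. Once-weekly dosing, the scheduled-day default, the unavoidable condition and the bar on extra doses together show that two full doses in the same few days are not intended. The shortest gaps need a dose 5 to 6 days early, or a late dose followed at once by an early one. If sites treat the window as symmetric and exactly 4 days as barred, no gap falls below 3 days. If the next scheduled dose is the first calendar one after dosing, late-then-early examples such as day 2 then day 4 fail.

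The harm is also inferred, since the documents give no toxicity rate for 40 mg over 1 to 2 days. That amount does not apply during titration, after dose reduction, or to subjects on placebo capsules. Diary review is more frequent before week 24 (weeks 4, 8, 12, 16 and 24), and rescued subjects have an extra visit with laboratory tests. Finally, the IPIM may state a minimum interval.

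Most of this stands as a limit on frequency and size. It does not close the gap. The neighbouring text sets no minimum: the unavoidable condition governs when a dose may move, not how far, and a scheduled dose taken early is not clearly an extra dose. A symmetric window is an assumption that the text does not make. The calendar reading still admits gaps of 1 to 2 days. The IPIM point affects where the correction comes from, because the protocol's own rule would still be incomplete.

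**Conclusion.** The concern holds. As written, the condition limits lateness to 2 or 3 days and does not limit earliness. The shortest gap that meets it is 1 day, against 4 or 5 days for a late dose followed by an on-time one. At maintenance dose, up to 40 mg can fall within that gap.

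This rests on whole-day dosing, on the protocol and SAP text alone, and on the IPIM being unseen. It does not claim that the protocol intends such dosing or that it would be common. Sample size, alpha, power and the primary analysis are unaffected. No harm is claimed for etanercept: its rule has the same form, but section 2.4 describes a trial that included 50 mg twice weekly. This is a low-frequency correction to a safety-relevant dosing instruction. It should be made because the rule does not secure the spacing that it is there to protect.

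**What to change.** In section 6.2.2.1, apply the 4-day limit in both directions by inserting *the previous dose actually taken or of* immediately before the reference to the next scheduled dose. State whether exactly 4 days is allowed.

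The minimum gap then becomes 4 days, or 5 if exactly 4 is not allowed. After an on-time dose, the next can move at most 7 - 4 = 3 days early, or 7 - 5 = 2. A maximally late dose followed by an on-time one still passes (7 - 3 = 4 meets a limit of at least 4; 7 - 2 = 5 exceeds 4), so no on-schedule dose is lost.

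Align the IPIM and the subject instructions. If the IPIM already gives a minimum interval, carry that figure into section 6.2.2.1. The 2-day wording in section 6.2.1.1 can be made symmetric for consistency only.

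The cost is one clause and matching instruction text. An occasional early dose would have to wait, at the latest until its scheduled day, or be skipped if it cannot be taken then or within the late window.
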